8.1 Sample Size

Sample size is based on:

- The primary efficacy variable -
 - Change from Baseline (score at Screening Part 1) to Week 12 for the Aberrant Behavior Checklist (ABC) subscale for Irritability
- The primary analysis set of Low-level FCT ITT subjects.
- 1:1 randomization scheme

Previously reported Sponsor data indicating that 60% of autistic children have pathologically low levels of FCT formed the basis for the following calculations. Assuming a -3.7 ± 7.0 ABC Irritability change from Baseline to Week 12 of for CM-AT and -0.6 ± 5.0 for Placebo, a sample size of 82 evaluable low-level subjects per treatment group (active and placebo) yields 90% power to declare a statistically significant difference between treatments at a two-sided 0.05 level of significance. To account for an anticipated 15% early withdrawal, 97 low-level subjects will be randomized per treatment group (active and placebo). A total of 162 subjects per group will be randomized to achieve 97 randomized low-level subjects per group (active and placebo).

8.2 General Statistical Issues

The primary efficacy analysis set is the Low-Level FCT ITT set defined in Section 3. Any efficacy analyses will be presented on other populations from Section 3 will be noted below. The primary safety analysis set is the Low-Level FCT Safety Analysis set. All safety analyses in the double-blind phase will be performed on this analysis set and, secondarily, on the entire Safety Analysis set defined in Section 3.

For quantitative (continuous) variables summaries will include the sample size, mean, median, standard deviation, minimum and maximum. For qualitative (i.e., categorical) variables, summaries will include the number and percent of subjects for each outcome.

Subjects may have a scheduled or unscheduled visit outside the protocol-specified time windows for any protocol-specified visit. Windows of scheduled visits will be expanded to have adjacent start/stop periods so that all visits (scheduled or unscheduled) fall within a scheduled visit window. For example, efficacy data are scheduled to be collected for each subject at screening, Baseline (Screening Part I), Randomization visit, and at Weeks 2, 4, 6, 8, 10 and 12 after randomization. The Week 2 visit will be expanded to allow any visit from 1 – 20 days post-randomization visit to be considered as the Week 2 visit. The Week 4 visit will be expanded to allow any visit from 21 – 34 days post-randomization visit to be considered as the Week 4 visit, etc.

Subjects may have more than one follow-up appointment that falls within a window for a given visit. In such a case, the follow-up data collected closest to the target date the visit should have occurred (given the number of weeks since randomization) will be used in the analysis. If two visits are equidistant from the target date of the scheduled visit, the later visit will be used in the analysis.

Pooling of study centers (i.e., combining study centers with small numbers of patients) may be required prior to performing efficacy analyses that include Study Center as a variable in the analysis. The following is the pooling algorithm that will be used (the algorithm described below is for the Low-Level FCT (≤12.6 U/g) analysis set; the algorithm will be repeated separately for every analysis set on which efficacy data will be analyzed):

If one or more study centers with Low-Level FCT (≤12.6 U/g) subjects have fewer than 10 subjects for the given analysis population, pooling of study centers will be required. Pooling of small study centers will be implemented as follows;

- Order the study centers, starting with those with the lowest numbers of Low-Level FCT (•12.6 U/g) subjects.
- The centers will then be combined in a consecutive upward order unless the total number of subjects exceeds the median number of subjects of all sites with 10 or more subjects.
- If this process does not capture all the study centers with fewer than 10 subjects, a second pooled study center will be created using the same process.
- This process will be continued until all study centers with fewer than 10 subjects are accounted for.

Again, this pooling algorithm will be repeated separately within each analysis population for which efficacy analyses will be run.

Unless otherwise indicated, p-values are two-sided and statistical significance is declared if the two-sided p-value is ≤ 0.05 . There is only one primary efficacy endpoint and one efficacy secondary endpoint. The primary endpoint will be tested at the two-sided 0.05 level of significance, and if significant, the secondary endpoint will be tested at the two-sided 0.05 level of significance. All other endpoints are considered exploratory and there will be no adjustment for multiple comparisons across these exploratory endpoints.

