Study Rationale:	Sponsor studies have demonstrated the clinical potential of CM-AT formulations in treating core and non-core autism symptoms in subjects with autism ages 3-8 with low fecal chymotrypsin (FCT) levels when dosed at a level of 900mg 3x daily.  This study will further quantify the changes in the target population as measured by standardized behavioral and quality of life tests, physiological measures, as well as characterize the efficacy and safety of the product. The study will further delineate the efficacy in a population that is biomarker negative (>12.6U/g of fecal chymotrypsin) who have autism.  The data from this study will help determine safety and efficacy of CM-AT in pediatric patients with autism of both biomarkers positive and negative.

	This study will be undertaken in children whose Aberrant Behavior Checklist: subscale for Irritability / Agitation (ABC-I) ≥11 is at Screening/Enrollment. This number represents those who fall above approximately 0.5 std deviations from the mean seen in the Sponsor's 00101 study.
Safety:	Fecal globin levels, the presence of occult blood, α 1 -antitrypsin, and weight loss will be used to monitor the safety and tolerability of CM-AT.
	
 
The presence of fecal globin may indicate bleeding in the large intestine, while a positive occult blood may indicate bleeding along the entire gastrointestinal tract.
 

	• An increase in α 1 -antitrypsin may signal an immunologic response of the colonic mucosa, leading to potential formation of colonic strictures.
	Weight loss may be indicative of malabsorption.
	
 
All of the above markers may be linked due to gastrointestinal irritation, but have not specifically been noted thus far in the Sponsor's experience with enzyme therapies.
 

	
 
Parental input at the standard visits, diary entries, and other assessments will also be used to monitor safety.
 

	
 
Of 468 children with autism given pancreatic enzymes in early Sponsor studies, and in the Phase III clinical studies (00101 & 00102), in which 180 were initially enrolled, and 140 continued into Open-Label, the drug appeared to be safe and well-tolerated with no related SAE experienced in either study the duration of which has been greater than 288 weeks. Primarily, AEs appeared to be GI in nature.
 

Rating Instruments:	ABC, SRS-2 (Preschool or School Age), PedsQL Inventory – Family Impact Module, CGI (S), CGI (I).

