## Exclusion Criteria:

Subjects who meet any of the following criteria will be excluded from study participation:

- 1. Patient weighing < 13kg
- 2. Allergy to porcine products
- 3. Previous sensitization or allergy to trypsin, pancreatin, or pancrelipase
- 4. History of severe head trauma, as defined by loss of consciousness or hospitalization, skull fracture or stroke.
- 5. Seizure within the last year prior to enrollment, or the use of seizure medications either at present or in the past.
- 6. Diagnosed with any of the following:
  - a. HIV-positive
  - b. Cancer (regardless of remission state)
  - c. Cerebral palsy
  - d. Muscular dystrophy
  - e. Known genetic disorder or abnormality
  - f. Blood dyscrasia
  - g. Ongoing gastrointestinal disease (e.g., Crohn's Disease, Celiac Disease. Not intended to exclude gastrointestinal issues, such as constipation or diarrhea not associated with another GI disease diagnosis.)
  - h. Endocrine disorder (e.g., hypothyroidism, diabetes)
  - i. Pancreatic disease (endocrine or exocrine)
  - j. Previous diagnosis with or hospitalization for significant co-morbid psychiatric conditions such as depression, bipolar or other psychiatric disease (Not intended to exclude ADHD, anxiety associated with autism or obsessive-compulsive disorder)
  - k. Any diagnosis of sleep or wakefulness disorder, such as narcolepsy, hypo or hypersomnia.
- 7. Evidence or history of severe, moderate or uncontrolled systemic disease, or history of metabolic disorders (e.g., amino acid deficiencies, hypoketosis)
- 8. Any co-morbid condition which in the Investigator's or Medical Director's opinion makes it undesirable for the subject to participate in the trial or would jeopardize compliance with the protocol.
- 9. Supplementation with any of the following within 30 days of entering the study:
  - a. Any enzyme product or a product containing pancreatic/digestive enzymes of plant or animal origin
  - b. Pancreatin, thyroid, or adrenal extracts, either synthetic, plant or animal-based
  - c. Essential fatty acids, omegas, or other supplement containing these products (does not require a washout)
  - d. Amino acids, or amino acid containing products
  - e. Any secretin product including transdermal, oral, or injectable
  - f. Vitamin B12/folate either oral or injectable (Allowable as part of a multivitamin. Folate not to exceed 400 mcg, B12 not to exceed 12 mcg). No injectables allowed of either.

	g. Chelating agents / chelation therapy

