Fecal Panel - For Fecal Chymotrypsin, pH and A1-Antitrypsin, descriptive statistics (number of subjects, mean, median, standard deviation, minimum and maximum) of Baseline (Screening Part I), each Post-Baseline visit and the change from Baseline at each Post-Baseline visit will be presented. Treatment groups will be compared on change from baseline at each visit using analysis of covariance adjusting for study center and Baseline. For Fecal Chymotrypsin, the number and percentage of subjects with values >12.6 U/g and \le 12.6 U/g at each visit will be presented. For pH, the incidence rate (number and percentage of subjects) with abnormal outcomes will be presented at each visit. For A1-Antitrypsin, the number and percentage of subjects with values <55 and ≥55 will be presented at each visit. Further, for fecal globin and fecal occult blood the incidence rate (number and percentage of subjects) with abnormal outcomes will be presented at each visit, where abnormal is defined as the variable being "present". No formal statistical hypothesis testing will be performed to compare the treatment groups on these results.

Vital signs – For each of the following measurements: weight (kg), systolic blood pressure (mmHg), diastolic blood pressure (mmHg) and pulse (beats per minute), descriptive statistics (number of subjects, mean, median, standard deviation, minimum and maximum) of Baseline, each Post-Baseline visit and the change from Baseline at each Post-Baseline visit will be presented. No formal statistical hypothesis testing will be performed to compare the treatment groups on these results.

Weight Loss by End of Study - The number and percentage of subjects losing weight by the end of the study will be tabulated for each visit for each treatment group. No formal statistical hypothesis testing will be performed

to compare the treatment groups on the proportion of subjects with weight loss.

9. Interim Efficacy Analysis

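### The closest-to-target visit rule has no safety exemption and stool abnormalities are counted only visit by visit, so an unscheduled positive result can be left out of the SAP 8.7 tables

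*SAP*

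**What the plan says.** SAP 8.2 (General Statistical Issues) widens the visit windows "so that all visits (scheduled or unscheduled) fall within a scheduled visit window". Its first example allows "any visit from 1 – 20 days post-randomization visit to be considered as the Week 2 visit"; the Week 4 window is days 21 to 34. When a window holds several appointments, the plan uses "the follow-up data collected closest to the target date the visit should have occurred". On ties: "If two visits are equidistant from the target date of the scheduled visit, the later visit will be used in the analysis". Efficacy visits are mentioned only as an example of the windowing.

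SAP 8.7 (Fecal Panel) says that "for fecal globin and fecal occult blood the incidence rate (number and percentage of subjects) with abnormal outcomes will be presented at each visit". Abnormal stool pH and A1-antitrypsin below 55 or at least 55 are likewise counted at each visit. Fecal chymotrypsin, pH and A1-antitrypsin also get descriptive change from Baseline and an analysis of covariance. Fecal globin and occult blood do not.

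The Protocol synopsis (Safety) names fecal globin, occult blood, A1-antitrypsin and weight loss as the monitoring markers and explains why, for example: "The presence of fecal globin may indicate bleeding in the large intestine". Its safety endpoints include the incidence of, or change in, these stool results. Exclusion criterion 6g is "Not intended to exclude gastrointestinal issues, such as constipation or diarrhea" that have no other GI disease diagnosis behind them.

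**The concern.** A rule that picks the record nearest the target day is reasonable for a mean at Week 4. It suits a safety marker less well, where the question is whether a child ever became abnormal on treatment. An unscheduled stool test may well be done because the child has symptoms, and it will usually lie further from the target day than the planned visit does.

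The by-visit tables then add a second gap. A percentage positive at each visit does not show how many different children were positive at some point. For fecal globin and occult blood it also does not separate a child who was already positive at Screening from one who became positive on treatment. Since children with constipation or diarrhea can enter, some Baseline abnormality is plausible. These are the markers that the protocol itself ties to bleeding, colonic mucosal response and malabsorption.

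**Working it through.** The plan gives no figure for this point, so there is none to reproduce. The windows and rules come from SAP 8.2; the spread of visit days is my assumption.

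**1. Does the rule reach safety data?** Section 8.2 covers both efficacy and safety analysis sets. Where it limits a rule to efficacy, as with pooling of centers, it says so. The window rule carries no such limit, and SAP 7.3 to 7.6 and 8.7 add no worst-value or all-results rule. As written, it applies.

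**2. One example.** Week 4 has target day 4 × 7 = 28. A scheduled negative test on day 27 is 1 day off; an unscheduled positive test on day 33 is 5 days off. Day 27 is used and day 33 is not.

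**3. How often the unscheduled result is dropped, given that both results are in the window.**
- W = days in the window: 20 (Week 2, target day 14) or 14 (Week 4, target day 28).
- The scheduled visit is s days from target, with s equally likely from −m to +m.
- The unscheduled result is equally likely on any of the other W − 1 days.
- The unscheduled result is kept if it is strictly closer to target, or tied and later. That is 0 days for s = 0, 2s − 1 days for s > 0, and 2|s| days for s < 0. For |s| up to 5, all these days lie inside both windows.

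For m = 3, the kept days over the seven offsets are 0 + (1 + 3 + 5) + (2 + 4 + 6) = 21.
- Week 4: 7 × 13 − 21 = 70 of 91 dropped = 76.9%.
- Week 2: 7 × 19 − 21 = 112 of 133 dropped = 84.2%.

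In general, the kept days sum to m² + m(m + 1) = m(2m + 1), out of (2m + 1)(W − 1). So the dropped share is 1 − m/(W − 1):

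| Spread of scheduled visit | Week 2 | Week 4 |
|---|---|---|
| ±1 day | 1 − 1/19 = 94.7% | 1 − 1/13 = 92.3% |
| ±3 days | 1 − 3/19 = 84.2% | 1 − 3/13 = 76.9% |
| ±5 days | 1 − 5/19 = 73.7% | 1 − 5/13 = 61.5% |

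**4. What the abnormality tables cover.**

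| Marker | By-visit count in 8.7 | Any-post-Baseline count in 8.7 | Relation to Baseline |
|---|---|---|---|
| Fecal globin, occult blood | yes | no | none |
| A1-antitrypsin, stool pH | yes | no | mean change only |
| Weight loss | yes | no | built into the definition (SAP 6.3) |

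**5. Why the by-visit count does not stand in for the per-child count.** Assume 2% of children are positive at each of k stool visits. If the same children are positive each time, 2% are ever positive. If visits are independent, the figure is 1 − 0.98^k: 5.9% for k = 3 and 11.4% for k = 6. In an arm of 162 that is 3.2 children (0.02 × 162) against 9.5 or 18.5. The same by-visit tables fit all of these. The 2% is only an illustration, and the SAP does not give k: section 7.3 says stool pH is taken at several visits, while section 6.3 says gastrointestinal measures are taken at each regular visit.

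**The case against.** The case against has real force on five points.

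- **The percentages are conditional.** They need a scheduled and an unscheduled result in one window. No document describes unscheduled stool testing, so the overall loss could be close to zero. If selection is made per variable, a lone unscheduled result is kept; the SAP does not say whether selection is per visit or per variable. This stands, and it limits how often the problem arises.
- **The rule is blind to result and arm.** It also drops later negative retests and keeps abnormal scheduled results. This stands: the documents show no built-in bias toward either arm.
- **Baseline is not ignored throughout.** The mean changes for pH and A1-antitrypsin and the definition of weight loss stand. A mean can still hide a few children who cross a threshold, and globin and occult blood have nothing comparable.
- **SAP 8.6.3 might supply an overall count.** It describes a count of dichotomous stool tests and then repeats it by visit, which could mean an any-time count comes first. The text is unclear, and the stool panel listed in SAP 6.3 omits fecal globin and occult blood.
- **There are other routes.** TEAE tables are not windowed, and data listings are mentioned. However, the only link that the SAP states from a finding to an AE form is the physical exam (7.2). Only the protocol synopsis is available, so a laboratory-to-AE rule elsewhere cannot be ruled out.

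**Conclusion.** The concern holds as a gap in safety reporting. It does not touch the primary efficacy analysis. Followed as written, SAP 8.2 leaves out the unscheduled stool result in about 77% (Week 4) or 84% (Week 2) of windows that hold one scheduled and one unscheduled result, with a range of 62% to 95%. This assumes scheduled visits spread evenly within ±3 days (range ±5 to ±1) and the unscheduled test equally likely on any other day. SAP 8.7 yields no count of children ever abnormal after Baseline, and for fecal globin and occult blood no way to tell new from pre-existing positivity.

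Two stronger readings are tempting, and the documents support neither. A reader might infer that positive findings vanish from the safety results altogether; they are lost from the by-visit stool tables, and anything reported as an AE still appears among the TEAEs. A reader might also infer that the by-visit tables shrink the difference between arms by a definite amount. That would require abnormality rates and persistence, which the documents do not give, and it would set one-visit prevalence against cumulative incidence, which are different quantities.

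**What to change.** In SAP 8.2, limit the closest-to-target rule to efficacy and to by-visit mean or mean-change summaries, and say whether selection is per visit or per variable.

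In SAP 8.7, descriptively and on both safety analysis sets, add:

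- (a) the number and percentage of children with any post-Baseline double-blind abnormality, using all scheduled and unscheduled results, for fecal globin, occult blood, A1-antitrypsin ≥55 and stool pH. Count pH as low (<5.92) and high (>8.00) separately, because a two-sided limit has no single worst value;
- (b) the same counts among children not abnormal at Baseline, with a shift table from Baseline to any post-Baseline status;
- (c) for weight, an any-post-Baseline loss count only. Loss is already a change from Baseline, so a shift table has no meaning there.

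The cost is SAP wording and a few tables from data already collected; no visits or tests are added. The downside is that counts using all results rise with how often a child is tested, so an arm tested less will look better. Report the number of tests per arm and a scheduled-only version next to each count.

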8.3 Subject Disposition

The number and percentage of subjects in each analysis set will be presented. With the exception of the Run-in Analysis Set and the All Randomized Analysis set, percentages will be based on the total number of randomized subjects who received study drug and had at least one post-Baseline ABC-I assessment (the ITT analysis set). For the All Randomized Analysis Set and the Run-in Analysis Set, no percentages will be presented; just the number of subjects will be presented. Randomized subjects without a baseline FCT measurement will not be counted in any Low-Level FCT (≤12.6 U/g) or Non-Low-Level FCT analysis set (>12.6 U/g) but will be included in all other analysis sets in which they reside.

Disposition of all subjects over the course of the double-blind portion of the trial will be presented for the Low-Level FCT ITT analysis set, the ITT analysis set, the Low-Level FCT All Randomized analysis set and the All Randomized analysis set. This presentation will include the number of subjects who completed the study through 12 weeks and the number who discontinued early as indicated on the End of Study Case Report Form page (along with the reason for study discontinuation as indicated on the same page).

The number and percent of subjects, by treatment group and overall, who discontinue during the double-blind phase will be summarized by reason for discontinuation. Percentages are based on the total number of subjects randomized in the given analysis set. The reasons for discontinuation as indicated on the End of Study Case Report Form page are:

- Adverse Event
- Noncompliance
- Protocol violation
- Withdrawal of consent

- Lost to follow-up
- Investigator decision
- Trial terminated by sponsor
- Other

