Subjects will be randomized to ensure 82 subjects per study arm of the low-level fecal chymotrypsin (FCT) children are evaluable for the primary statistical analysis (treatment comparison on the primary endpoint of change in ABC irritability from Baseline to Week 12 on the primary analysis set of children with FCT \leq 12.6 in randomized subjects). The FCT value used in determination of whether the patient has FCT \leq 12.6 is the Screening Part 1 value; if the patient has more than one screening FCT, the last FCT measured prior to randomization will be used to determine whether the patient has FCT \leq 12.6. It is anticipated that each site will enroll approximately 3 to 5 subjects per month and the study will be open for a period of twelve months. A power recalculation may be performed midway through Study Protocol 00103 to determine if sufficient numbers of biomarker negative children have been enrolled.

A subject may enroll in Study Protocol 00104 Open Label Extension after successfully completing Week 12 of Study Protocol 00103. The analyses of data collected in Study Protocol 00104 Open Label Extension will be discussed in a separate analysis plan.

3. Study Analysis Sets

One-hundred sixty-two (162) subjects will be randomized per treatment arm, or 324 subjects total. These subjects will be randomized from approximately 35 sites throughout the United States. Approximately 350 subjects will be enrolled into the placebo run-in period to ensure that 324 will be randomized. At the completion of the two-week placebo run-in, the subject will be assessed for compliance and ABC-I scores. If a subject's score on the ABC-I scale has increased or decreased by 30% or more, or is <9 on the retest, they will be discontinued from the study and not randomized.

The study population will consist of children, both males and females, between 3 and 8 years of age inclusively at the time of consent. All study participants must have an initial ABC-I score of ≥ 11 and a diagnosis of Autistic Disorder as demonstrated by the DSM-IV-TR and by the ADI-R. Subjects will also be screened using the SCQ and must achieve a score of ≥ 15 to be considered eligible.

The following populations form the basis of the analysis sets that will be included in efficacy and safety analyses (not listed in order of analysis below. For order of analysis see Section 6.0):

Intent-to-Treat (ITT): All randomized subjects who received study drug and had at least one post-Baseline ABC-I assessment.

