Low-level FCT ITT: All randomized subjects with pathologically low levels of FCT (≤12.6 U/g) who received study drug and had at least one post-Baseline ABC-I assessment. Subjects are analyzed under the treatment to which they are randomized. This is the primary analysis population for efficacy.

Non-Low-Level FCT (FCT >12.6) ITT: All non-low-level (FCT >12.6 U/g) randomized subjects who received study drug and had at least one post-Baseline ABC-I assessment. Subjects are analyzed under the treatment to which they are randomized. This is an exploratory analysis population for efficacy.

All Randomized: All randomized subjects. This is an exploratory analysis population for efficacy. Subjects are analyzed under the treatment to which they are randomized.

Low-level FCT All Randomized Subjects: All randomized subjects with pathologically low levels of FCT (≤12.6 U/g). This is a population for use in a sensitivity analysis of efficacy. Subjects are analyzed under the treatment to which they are randomized.

Non-Low-Level FCT (FCT >12.6) All Randomized Subjects: All non-low-level (FCT >12.6 U/g) randomized subjects. Subjects are analyzed under the treatment to which they are randomized. This is an exploratory analysis population for efficacy.

Per-Protocol (PP): All ITT subjects who have completed a Week 12 visit and have a Week 12 ABC-I score. Subjects are analyzed under the treatment to which they are randomized. This is an exploratory analysis population for efficacy.

Low-Level FCT (FCT \leq 12.6) Per Protocol (PP): All low-level (FCT \leq 12.6 U/g) PP Subjects. Subjects are analyzed under the treatment to which they are randomized. This is an exploratory analysis population for efficacy.

Non-Low-Level FCT (FCT >12.6) PP: All non-low-level (FCT >12.6 U/g) PP Subjects. Subjects are analyzed under the treatment to which they are randomized. This is an exploratory analysis population for efficacy.

Run-in Analysis Set: All subjects receiving at least one dose of placebo during the placebo-run in phase. All subjects will be analyzed as one group.

Safety Analysis Set: All subjects receiving at least one dose of randomized treatment. Subjects are analyzed under the treatment received. This is a primary analysis set for safety.

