Low-Level FCT (FCT \leq 12.6) Safety Analysis Set: All Low-Level subjects (FCT \leq 12.6) receiving at least one dose of randomized treatment. Subjects are analyzed under the treatment received. This is the secondary analysis set for safety.

4. Test product, Dose and Mode of Administration

900mg of CM-AT (pancreatic enzyme concentrate encapsulated in hydrogenated soybean oil) 3x daily sprinkled over food. To be taken with a meal or large snack.

5. Demographics, Other Baseline Characteristics (other than efficacy and safety variables), Study Drug Compliance

"Baseline" for variables other than efficacy and safety refers to the last value of the variable measured prior to start of randomized treatment. For efficacy and safety, "Baseline" is defined as the value measured at Screening Part 1, denoted as "Screening" below.

- 5.1 Demographics Baseline demographics of age, gender (male; female), ethnicity (Hispanic or Latino; not Hispanic or Latino), race (American Indian or Alaska Native; Asian; Black or African American; Native Hawaiian or other Pacific Islander); height (cm), weight (kg), body mass index (BMI).
- 5.2 Physical examination abnormalities by body system (HEENT, Respiratory, Cardiovascular, Abdomen, Musculoskeletal, Central Nervous System, Dermatologic, General Appearance, Other)
- 5.3 Responses to each question on Study Specific Medical History questionnaire
- 5.4 Response to each question on Neurodevelopmental history questionnaire
- 5.5 Responses to each question on Family History questionnaire
- 5.6 Responses to each question on Parent Visit questionnaire
- 5.7 Screening ABC-I score. The scoring of this subscale is given in Appendix A.
- 5.8 Screening DSM-IV-TR total score and sub-scores (Social Interaction; Communication; Behavior) as described in Appendix C.

- 5.9 Screening SCQ total score and sub-scores (Social Interaction; Communication; Restricted, Repetitive, and Stereotyped Patterns of Behavior).
 - The total score and the subscales of Reciprocal Social Interaction, Communication, and Restricted, Repetitive, and Stereotyped Patterns of Behavior domain are given in Appendix B.
- 5.10 Screening ADI-R (Total A, Verbal Total B, Nonverbal Total B, Total C and Total D). These scores are determined by the rater and recorded directly on the questionnaire.

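### SAP 8.3 sizes four analysis sets against an ITT count that does not contain them, so the Safety set can print above 100% and retention from randomisation is not shown as a percentage

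*SAP*

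**What the plan says.** SAP 8.3 plans a table with the number and percentage of subjects in each analysis set. The denominator rule opens "With the exception of the Run-in Analysis Set and the All Randomized Analysis set" and continues that "percentages will be based on the total number of randomized subjects who received study drug and had at least one post-Baseline ABC-I assessment". For the two exempt sets, "no percentages will be presented; just the number of subjects will be presented".

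The sets are defined in SAP Section 3:

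- The denominator: "Intent-to-Treat (ITT): All randomized subjects who received study drug and had at least one post-Baseline ABC-I assessment".
- "Safety Analysis Set: All subjects receiving at least one dose of randomized treatment", with no ABC-I requirement.
- Low-Level Safety: low-FCT subjects "receiving at least one dose of randomized treatment. Subjects are analyzed under the treatment received. This is the secondary analysis set for safety".
- "Low-level FCT All Randomized Subjects: All randomized subjects with pathologically low levels of FCT", with no dosing or ABC-I requirement.
- Non-Low-Level All Randomized: "All non-low-level (FCT >12.6 U/g) randomized subjects. Subjects are analyzed under the treatment to which they are randomized".

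SAP 8.3 adds that a randomised child with no baseline FCT value is counted in neither the low-level nor the non-low-level sets.

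The same section separately plans completion and early discontinuation for the Low-Level ITT, ITT, Low-Level All Randomized and All Randomized sets. Reasons for discontinuation are given by treatment group, as a percentage of those randomised in the set concerned.

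**The concern.** A percentage describes a share only if the numerator is contained in the denominator. ITT adds two conditions to randomisation: dosing, and a post-Baseline ABC-I. Safety drops the second condition, and the two FCT-specific randomised sets drop both. The rule can therefore print a share above 100% for Safety and overstated shares for the FCT-specific randomised and Low-Level Safety sets. ITT reads 100% whatever was lost before it.

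The primary efficacy set, Low-Level FCT ITT, leaves out randomised children without a qualifying ABC-I. A reader judging bias from that exclusion wants the proportion left out, by arm. This is the natural table to show it, and under the stated rule no percentage in it does so directly.

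**Working it through.** **Containment, from the definitions in SAP Section 3**

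| Set | Must be dosed | Must have post-Baseline ABC-I | Subset of ITT |
|---|---|---|---|
| ITT | yes | yes | is the denominator |
| Low-Level ITT, Non-Low-Level ITT, all PP sets | yes | yes | yes |
| Safety, Low-Level Safety | yes | no | no |
| Low-Level and Non-Low-Level All Randomized | no | no | no |

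The exemption in SAP 8.3 names All Randomized but not its two FCT-specific counterparts, so the ITT denominator applies to them.

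**Base for the illustration.** SAP 8.3 states no figure of its own, so I use the planned size from SAP 8.1 and Section 3, which reproduces. For a difference of 3.7 − 0.6 = 3.1 and SD √((7² + 5²)/2) = 6.083, 82 per group gives t-test power of 0.900. Then 82/0.85 = 96.5, rounded up to 97 low-level per group; 97/0.60 = 161.7, rounded up to 162 per group; total 2 × 162 = 324. Low-level randomised: 2 × 97 = 194. Non-low-level: 324 − 194 = 130.

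**Assumptions.** All 324 are dosed and have an FCT value, and post-Baseline means after randomisation. The documents give no rate for children without such an ABC-I, so I vary it from 0 to 15%. The upper end borrows the 15% early-withdrawal allowance in SAP 8.1.

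**Formulas.** With m children lacking the score (rounded to whole children), ITT = 324 − m. Printed Safety % = 100 × 324/ITT. Printed Low-Level All Randomized % = 100 × 194/ITT. Printed Non-Low-Level All Randomized % = 100 × 130/ITT. True retention = 100 × ITT/324.

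| Assumed share missing | m | ITT | Safety, printed | Low-Level All Rand., printed | Non-Low-Level All Rand., printed | ITT, printed | ITT as % of randomised |
|---|---|---|---|---|---|---|---|
| 0% | 0 | 324 | 100.0 | 59.9 | 40.1 | 100 | 100.0 |
| 1% | 3 | 321 | 100.9 | 60.4 | 40.5 | 100 | 99.1 |
| 2% | 6 | 318 | 101.9 | 61.0 | 40.9 | 100 | 98.1 |
| 3% | 10 | 314 | 103.2 | 61.8 | 41.4 | 100 | 96.9 |
| 5% | 16 | 308 | 105.2 | 63.0 | 42.2 | 100 | 95.1 |
| 10% | 32 | 292 | 111.0 | 66.4 | 44.5 | 100 | 90.1 |
| 15% | 49 | 275 | 117.8 | 70.5 | 47.3 | 100 | 84.9 |

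The true low-level share of those randomised is 194/324 = 59.9% in every row. With everyone dosed, Low-Level Safety is also 194 and prints the same inflated figure as Low-Level All Randomized. The two FCT-specific randomised sets together print 324/ITT, the same excess as Safety.

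**Which denominator repairs it.** At 5%, about 10 of the 194 low-level children are lost, leaving 184 in Low-Level ITT. Against All Randomized that reads 184/324 = 56.8%, which mixes the prevalence of low FCT with the loss. Against Low-Level All Randomized it reads 184/194 = 94.8%, which is the retention wanted.

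**The case against.** A reader might infer that the plan hides the loss between randomisation and analysis. It does not.

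- The All Randomized and ITT counts are both printed in this table, so the loss follows by subtraction.
- Low-Level ITT and Low-Level All Randomized share a denominator, so the ratio of their printed percentages gives retention in the primary set: at 5%, 59.7/63.0 = 94.8%.
- SAP 8.4 summarises demographics by treatment group for the same ITT and randomised sets, and SAP 8.2 includes the sample size in continuous summaries, so per-arm counts are available.
- Discontinuation is already reported on randomised denominators. That does not fully replace retention, because a child who stops after one assessment stays in ITT.
- The children left out of ITT are not ignored in the analysis. SAP Section 3 assigns Low-Level All Randomized to a sensitivity analysis, and SAP 8.6 runs the efficacy analyses on every All Randomized set.

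A second objection concerns wording. The SAP defines the efficacy Baseline as Screening Part 1, and the ABC-I is repeated at the randomisation visit, where it decides eligibility. Read literally, that retest is post-Baseline, nearly every dosed child is in ITT, and Safety prints at about 100%. This is fair: the excess above 100% depends on the post-randomisation reading. That reading is evidently the intended one, and the protocol itself labels Visit 1 as Baseline, but the SAP does not say so. On the literal reading a smaller fault remains, because children randomised but never dosed are absent from the denominator. If 1% are undosed and nothing else is lost, Safety reads 100.0%, Low-Level All Randomized reads 60.4% against 59.9%, and ITT still reads 100% when it is 99.1% of those randomised.

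The missing-score rates are assumptions, and at low rates the distortion is small.

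**Conclusion.** The denominator rule is wrong as written for four sets, by the SAP's own definitions. Under the post-randomisation reading, Safety exceeds 100% once a single dosed child lacks a later ABC-I: about 103% at an assumed 3%, 105% at 5%, and 118% at the 15% upper end. Low-Level All Randomized prints between 60.4% and 70.5% over the 1 to 15% range, against a true 59.9%. Retention from randomisation to the analysis sets is not shown as a percentage, although it can be derived from the printed counts.

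This is a reporting error of minor weight. It does not touch the sample size, power, alpha, the primary model or its result, and it does not show that any loss is concealed.

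**What to change.** In SAP 8.3, replace the ITT denominator, by arm and overall, as follows:

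1. ITT, PP and Safety as a percentage of All Randomized.
2. Each Low-Level set as a percentage of Low-Level All Randomized, and each Non-Low-Level set as a percentage of Non-Low-Level All Randomized. All Randomized should not serve as the single denominator for these, for the reason shown in the working.
3. Run-in remains a count only.

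In SAP Section 3, state that post-Baseline in the ITT definitions means after randomisation.

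Add a footnote that Safety is grouped by treatment received while the denominator is grouped by treatment assigned. A by-arm Safety percentage can therefore differ, and could still pass 100%, if a child received the other treatment.

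The cost is a few sentences and one table shell. No extra data or analysis is needed, and SAP 8.3 already uses randomised denominators for discontinuation reasons.
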